2.4 Are there any risks to the participants involved in the trial?

Critically ill patients with AKI who are started on CRRT and enrolled in this trial are unlikely to encounter incremental risk beyond that experienced in the ICU.[26, 27] This trial will measure adverse and serious adverse events to ensure patients are exposed to minimal risk in the trial.

2.5 Objectives

The overall WISDOM trial program will address whether a lower CRRT dose-intensity in critically ill patients with AKI is non-inferior to standard CRRT dose-intensity and will secondarily address whether lower CRRT dose intensity will shorten total CRRT duration and improve kidney recovery compared with standard CRRT dose-intensity. This pilot trial will specifically evaluate the feasibility of lower versus standard CRRT dose-intensity.

3. METHODS: PARTICIPANTS, INTERVENTIONS, AND OUTCOMES

3.1 Trial Design

This LoW Dose-Intensity vs. Standard Dose-Intensity Continuous Renal ReplaceMent Therapy in Critically Ill Patients (WISDOM) trial is a multicentre prospective, randomized, open-label, blinded endpoint (PROBE) pilot trial in adult ICU patients with AKI receiving CRRT.

3.2 Study Setting

The WISDOM pilot trial will take place at sites across Canada and internationally, most of which participated in the international STARRT-AKI trial.[10] These will include a spectrum of academic/teaching and community ICU sites.

3.3 Eligibility Criteria

Patients who are admitted to an ICU and are prescribed CRRT will be potentially eligible and will be identified through local site processes. Each patient will be further assessed for the presence of all inclusion and exclusion criteria. Those patients fulfilling eligibility will be approached (most often this will be an authorized representative or surrogate decision-maker [SDM]) by a member of the treating ICU team and/or a research coordinator to invite participation and obtain informed consent. Each patient or SDM will be provided an information sheet with details of the trial and a copy of the consent form. Consent will be sought from all patients for linkage to routinely collected administrative health data to measure long-term outcomes and to contact patients or SDMs for information related to the outcome of the trial.

3.3.1 Inclusion Criteria

Eligible patients will be admitted to an intensive care unit and fulfill the following inclusion criteria:

- i) age \geq 18 years
- ii) patient weight \geq 55 kg
- iii) plan to initiate CRRT or within 24 hours of having started CRRT for AKI
- iv) expected to survive and receive CRRT for a duration of \geq 48 hours
- v) able to provide informed consent or have an authorized representative provide consent after being informed of the details and risks of the trial unless a deferred consent process is approved by the local Research Ethics Board (REB).

3.3.2 Exclusion Criteria

At the time of screening, any of the following criteria will result in exclusion:

- i) indication for sustained higher dose-intensity CRRT as designated by the attending clinician(s)
- ii) end-stage kidney disease receiving maintenance dialysis
- iii) receipt of any RRT for AKI during the current hospitalization
- iv) inability to comply with the requirements of the study protocol

This trial does not restrict co-enrollment on other clinical trials unless the intervention in the other trial is perceived to interact with the WISDOM interventions. This will be determined by the PIs.

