Background:	An estimated 12-15% of critically ill patients receive RRT for acute kidney injury, the majority of whom initially receive continuous renal replacement therapy (CRRT). The 2012 Kidney Disease: Improving Global Outcomes (KDIGO) Clinical Practice Guidelines (CPG) for AKI recommend delivering a CRRT dose-intensity of 20-25 mL/kg/hr. This recommendation is derived from prior RCTs evaluating higher dose-intensity (35-40 mL/kg/hr vs. 20-25 mL/kg/hr) that have not shown any survival advantage. These findings translated to a dose-intensity of 20-25 mL/kg/hr becoming the de facto dose-intensity standard for patients receiving CRRT. In addition, because epidemiologic studies describing CRRT dose-intensity practices have consistently found that the “delivered” dose-intensity was often less than “prescribed” (only ~75-90%), usually due to therapy interruptions (i.e., circuit clotting; diagnostic imaging; minor surgical procedures), the 2012 KDIGO CPGs suggest that dose-intensity augmentation is required and that “ a higher prescription ” in the range of 25-30 mL/kg/hr is needed. The current practice, based on data from ICUs in Alberta, Canada and sites that participated in the international STARRT-AKI trial shows the range in median delivered CRRT dose-intensity is 26-30 mL/kg/hr. To date, no RCT has focused on evaluating or defining a minimally acceptable and safe CRRT dose-intensity threshold. Specifically, it is not clear whether a lower dose-intensity (10-15 mL/kg/hr) may be equally acceptable or even superior to the current guideline-directed standard (25-30 mL/kg/hr).
Objective:	The WISDOM research program aims to address whether a lower CRRT dose-intensity (10-15 mL/kg/hr) in critically ill patients with AKI is non-inferior for 90-day mortality compared to the current guideline-directed standard CRRT dose-intensity (25-30 mL/kg/hr) and will secondarily determine if lower CRRT dose-intensity can shorten RRT duration and improve kidney recovery versus the guideline-directed standard.
Study Design:	Multi-centre prospective, randomized, open-label, blinded endpoint (PROBE) pilot trial in adult ICU patients with AKI receiving CRRT.
Population:	ICU patients with AKI in whom the clinical team has decided to start CRRT or who are within 24 hours of having started CRRT will be potentially eligible. Each patient will fulfill all inclusion and have no exclusion criteria.
Eligibility:	Inclusion criteria:

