3.4 Interventions

3.4.1 Study Interventions

All enrolled patients will receive the standard dose-intensity for a maximum of 24 hours and a minimum of 12 hours from the time CRRT is started (not the time of enrollment and randomization) to ensure initial metabolic and azotemic stabilization.

The *experimental arm* will be lower CRRT dose-intensity, defined by a delivered effluent flow rate of **10-15 mL/kg/hr**. The rationale for this lower dose-intensity is based on the observed lower threshold currently delivered in clinical practice and observational data showing that this threshold is acceptable, tolerated and safe.[26-28] The *control arm* will be guideline-directed standard CRRT dose-intensity, defined by a delivered effluent flow rate of **25-30 mL/kg/hr**. The standard dose-intensity aligns with current practice and by recommendations from international CPGs.[31] The standard of care for CRRT dose-intensity provided in ICUs in Alberta in a recent audit and across participating sites in STARRT-AKI (39 Canadian sites) ranged between 26-30 mL/kg/hr. The dose calculation will utilize measured or estimated actual body weight.

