3.5.2 Secondary Endpoints

The secondary feasibility endpoints are:

- i) Ability to enroll an average of 2 patients per site per month. We believe a target of 2 per month is feasible across sites in Alberta given the number of patients starting CRRT per month (~32 new CRRT initiations per month) and accrual at sites during the STARRT-AKI trial.
- ii) The ability to enroll >50% of fully eligible patients.
- iii) Time from eligibility (e.g., starting RRT) to randomization with a target of >75% of eligible patients within 12 hours.
- iv) Protocol adherence for allocated CRRT dose-intensity. We believe a target in-range dose-intensity of >80% to be adequate.
- v) Ability to capture delivered CRRT dose-intensity measures. This is a process measure of trial implementation and fidelity. We believe a target of electronic capturing >95% of daily time-averaged CRRT dose-intensity data to be adequate. This will enable an assessment of difference in CRRT dose-intensity between groups.
- vi) Ability to capture patient and kidney endpoints at 90-days from randomization. We believe a target of >95% ascertainment to be adequate.

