3.6 Sample size calculation and recruitment

For the WISDOM pilot trial, our primary sample size consideration will address the detection of a minimum difference in the delivered dose-intensity of CRRT between the groups. For the WISDOM pilot trial, we are targeting a total sample size of 100 patients (50 patients per group). This is based on the ability to detect a minimum difference of 10 mL/kg/hr in dose-intensity, assuming delivery of 25 mL/kg/hr in the standard dose-intensity group and 15 mL/kg/hr in the lower dose-intensity group, with a conservative standard deviation (SD) of 15, 90% power, and an alpha of 0.05. This would translate into a sample of 96 patients (48 patients per group) that will be inflated to 100 to account for any withdrawal or dropout (See Table below).

Table. Sample Size Calculation Estimates.

Scenario	Difference in Dose Intensity	Standard Deviation	Power	Estimated Sample (Total)
1	10	5.0	0.9	12
2	10	7.5	0.9	24
3	10	10.0	0.9	44
4	10	12.5	0.9	66
5	10	15.0	0.9	96
6 (ATN Trial)	15	6.3*	0.9	18
7 (RENAL Trial)	15	15.3**	0.9	100
* From the ATN trial, based on average standard deviation for both groups of the aggregate total effluent flow rate delivered.[18]				
** From the RENAL trial, based on average standard deviation for both groups of the aggregate total effluent flow rate delivered.[17]				

For the WISDOM pilot trial, the total sample of 100 patients would translate into a target recruitment of 4 patients per week (50% of expected eligible) across 5-10 sites, thereby requiring an estimated 6-10 months to complete, if all sites are active.

We will further explore the practicality of identification of eligible patients, site-specific recruitment, protocol adherence, and data monitoring and ascertainment, that will inform the logistical planning and operations of a larger-scale multi-centre trial.[34]

All patients enrolled in the trial will be admitted to and monitored in an ICU setting. The primary and secondary feasibility endpoints, along with biochemical and process of care endpoints will be captured in local hospital medical records (either paper charts or electronic medical records) and data repositories. Data will be captured electronically where feasible, otherwise, standardized paper case report forms will be used. The expected rate of loss to follow-up will be low for ICU and hospital-specific outcomes

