7.4 Protocol Deviations

A protocol deviation is any noncompliance with the clinical trial protocol, International Conference on Harmonisation Good Clinical Practice (ICH GCP), or Manual of Procedures (MOP) requirements. The noncompliance may be either on the part of the participant, the investigator, or the study site staff. As a result of deviations, corrective actions may need to be developed by the site and implemented promptly.

These practices are consistent with ICH GCP E6 (R2):

- 4.5 Compliance with Protocol, sections 4.5.1, 4.5.2, and 4.5.3
- 5.1 Quality Assurance and Quality Control, section 5.1.1
- 5.20 Noncompliance, sections 5.20.1, and 5.20.2.

It is the responsibility of the site investigator to use continuous vigilance to identify and report deviations. All deviations must be addressed in the source documents and reported in the participant database as soon as the study team is aware of the deviation. Protocol deviations must be sent to the local REB per their policies. The site investigator is responsible for knowing and adhering to the reviewing REB requirements.

Examples of protocol deviations which may occur (but are not limited to) include:

- Consent Procedures error: no consent/re-consent obtained (deferred, SDM/participant or regained capacity), incorrect consent form used, not all signatures obtained, etc
- Inclusion/Exclusion criteria not met
- Study Procedures: did not begin receiving study-prescribed CRRT within the protocol specified timelines, received incorrect CRRT prescription, CRRT dose escalated above the protocol-mandated dose-intensity target
- Confidentiality Breach
- SAE Reporting: Did not notify coordinating centre of SAE within 24 hours of becoming aware

There may be other types of deviations that occur as well. All deviations should be recorded in the REDCap participant database. Further details about the handling of protocol deviations are included in the MOP.

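### Exclusion iii, applied at screening with no exception for the qualifying CRRT course, bars every patient first screened after CRRT start, a route that inclusion iii expressly admits

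*Protocol*

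**What the plan says.** Inclusion iii in section 3.3.1 gives two ways in: "plan to initiate CRRT or within 24 hours of having started CRRT for AKI". The Summary repeats it under Eligibility, and its Population entry states that patients "who are within 24 hours of having started CRRT will be potentially eligible".

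Section 3.3.2 opens with "At the time of screening, any of the following criteria will result in exclusion". Item iii of that list is "receipt of any RRT for AKI during the current hospitalization". The Summary carries the same item in the same words.

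Two other sections show that enrolment after CRRT start is expected. Section 3.4.1 counts the standard-dose run-in from CRRT start rather than from enrolment or randomization. Secondary feasibility endpoint iii in section 3.5.2 is "Time from eligibility (e.g., starting RRT) to randomization with a target of >75% of eligible patients within 12 hours".

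Section 7.4 lists "Inclusion/Exclusion criteria not met" among its examples of protocol deviations.

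**The concern.** CRRT is a form of RRT; section 2.1 introduces it as such. A patient screened six hours after starting CRRT for AKI therefore satisfies inclusion iii and, by virtue of the same treatment, meets exclusion iii. Nothing in the protocol exempts the qualifying course or confines the exclusion to earlier RRT. Because the Summary and the body agree word for word on exclusion iii, neither can be used to correct the other.

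This is a feasibility pilot, so who counts as eligible is part of what is being measured. Three things depend on a single definition:

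- the target in 3.5.2 of enrolling more than half of fully eligible patients;
- the screening log in 3.6, which records eligible patients who were not randomized and is meant to monitor selection bias;
- the count of eligibility deviations under 7.4, all of which must be recorded in REDCap and sent to the local REB according to its policies.

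Sites that read exclusion iii differently would enrol different populations and report different denominators.

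**Working it through.** **Comparison of the criteria**

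| Patient at first screening | Inclusion iii | Exclusion iii, read literally | Result |
|---|---|---|---|
| CRRT planned, no RRT yet | met | not met | eligible |
| On CRRT for AKI for 24 hours or less, no earlier RRT | met | met | admitted and excluded |
| On CRRT for AKI for 24 hours or less, with an intermittent session or separate CRRT course earlier in the stay | met | met | excluded, as the criterion presumably intends |

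The contradiction lies in the second row. All patients in that row are barred, and none in the first row are. The test is made at screening, so a patient screened while CRRT is only planned, and randomized some hours after it starts, stays in the first row.

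Endpoint iii in 3.5.2 gives starting RRT as the example of becoming eligible. Under exclusion iii, starting RRT makes a patient who has not yet been screened ineligible.

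**The plan's own figures**

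Sample size (3.6): difference 10 mL/kg/hr, SD 15, power 90%, alpha 0.05 (taken as two-sided). With the normal approximation, n per group = 2 × (1.960 + 1.282)² × 15² / 10² = 47.3, rounded up to 48, or 96 in total. This matches the stated 96, later inflated to 100, and eligibility does not enter it.

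Accrual (3.6): "target recruitment of 4 patients per week (50% of expected eligible) across 5-10 sites". Four per week at 50% implies 4 / 0.5 = 8 eligible per week. Then 100 / 4 = 25 weeks, and 25 / (52/12) = 5.8 months, close to the lower end of the stated 6-10 months.

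**Effect of literal application**

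Let f be the share of eligible patients already on CRRT when first screened. The protocol gives no value, so f is an assumption and could lie anywhere from 0 to 1. Assume also that the 50% enrolment fraction is the same for both routes and that sites do not move screening earlier.

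Weekly accrual = 0.5 × 8 × (1 − f). Weeks to 100 patients = 100 / weekly accrual.

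| f (assumed) | Enrolled per week | Weeks to 100 | Months |
|---|---|---|---|
| 0 | 4 | 25 | 5.8 |
| 0.25 | 3 | 33.3 | 7.7 |
| 0.50 | 2 | 50 | 11.5 |
| 0.75 | 1 | 100 | 23 |

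The upper limit of 10 months is 10 × 52/12 = 43.3 weeks, which needs 100 / 43.3 = 2.31 patients per week. Setting 4 × (1 − f) = 2.31 gives f = 0.42.

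**The case against.** The best defence is that no sensible site would apply exclusion iii to the very CRRT that qualifies the patient. Doing so would cancel half of inclusion iii and contradict the Population entry. Sites receive protocol training at an initiation visit (7.5), eligibility eCRFs must be submitted before randomization (7.6), and the screening log records reasons for exclusion (3.6), so divergent use would show up. A site that did read the rule literally could screen at the planning stage, which inclusion iii allows.

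This makes the long recruitment times unlikely in practice and limits divergence between sites. It does not remove the contradiction: the text says any RRT, no section narrows it, and sites across Canada and internationally should not each have to guess the intended meaning.

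Three stronger readings are tempting, and the documents do not support them:

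- **Most of the intended population is ineligible.** That needs f above 0.5. Sections 3.4.1 and 3.5.2 show that enrolment after CRRT start is expected, but say nothing about how many patients are first screened after it. At f = 0.25 recruitment would still finish within 6-10 months.
- **Everyone randomized after CRRT start breaches exclusion iii.** The criterion is tested at screening, so only patients first screened after CRRT start are caught. No number of deviations among the 100 patients can be derived.
- **The enrolment rate per site per month becomes uninterpretable.** That rate has no eligible-patient denominator. Literal use could lower it at some sites, but its meaning would not change.

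**Conclusion.** The concern holds as a contradiction between two current eligibility criteria, present in both the Summary and the body. Exclusion iii as worded bars the whole of one entry route that inclusion iii and the Population entry open, namely patients first screened after CRRT start. The planned-CRRT route is untouched.

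The size is not known, because the share of patients on the barred route is not stated. The recruitment times above are conditional on an assumed f, on literal application, and on unchanged screening practice; under those conditions the stated duration fails once f exceeds about 0.42. Independently of f, inconsistent readings would blur the denominator for the more-than-50% target, the screening log and the deviation count. The calculation of 96 patients, inflated to 100, stands.

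**What to change.** Reconcile inclusion iii and exclusion iii in 3.3.1, 3.3.2 and the Summary by stating whether the qualifying CRRT course counts as excluding RRT. If the already-started route is meant to stay open, as the Population entry indicates, exclusion iii could be limited to RRT for AKI received in this hospitalization before the present CRRT course. Use the same wording in the eligibility eCRF and in the screening log's definition of an eligible patient, so that the more-than-50% target and the 7.4 deviations are counted alike at every site.

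The cost is one clause in a protocol amendment, with the usual REB review and site notification, and matching edits to the eCRF and the log. No patients, visits or procedures are added, and the sample size does not change.

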3.4 Interventions

3.4.1 Study Interventions

All enrolled patients will receive the standard dose-intensity for a maximum of 24 hours and a minimum of 12 hours from the time CRRT is started (not the time of enrollment and randomization) to ensure initial metabolic and azotemic stabilization.

The *experimental arm* will be lower CRRT dose-intensity, defined by a delivered effluent flow rate of **10-15 mL/kg/hr**. The rationale for this lower dose-intensity is based on the observed lower threshold currently delivered in clinical practice and observational data showing that this threshold is acceptable, tolerated and safe.[26-28] The *control arm* will be guideline-directed standard CRRT dose-intensity, defined by a delivered effluent flow rate of **25-30 mL/kg/hr**. The standard dose-intensity aligns with current practice and by recommendations from international CPGs.[31] The standard of care for CRRT dose-intensity provided in ICUs in Alberta in a recent audit and across participating sites in STARRT-AKI (39 Canadian sites) ranged between 26-30 mL/kg/hr. The dose calculation will utilize measured or estimated actual body weight.

3.4.2 Criteria for discontinuing or modifying allocated interventions

The duration of the intervention will be until CRRT is discontinued due to any of patient death, transition to intermittent RRT (IRRT) or due to kidney recovery with no further requirement for RRT. Transition to IRRT will align with current best practices and align with local standards of care. This will generally occur following hemodynamic stabilization and weaning of vasoactive support (i.e., SOFA_{CV} score <2). Ultimate decisions about transitions to IRRT will be made by the local attending physicians. If during their ICU admission a patient has their CRRT temporarily interrupted (e.g., diagnostic imaging or other investigations; procedures or operations), once restarted, the CRRT will be prescribed according to their allocated dose-intensity. If a patient has prolonged CRRT interruption (>6 hours) (e.g., operative theatre), CRRT will be temporarily restarted at the standard dose-intensity for 6 hours to ensure a period of stabilization, then transitioned to their allocated CRRT dose-intensity, as applicable.

If patients are perceived by the treating ICU team to require a temporary increase in dose-intensity to augment acid-base/metabolic/azotemic control due to critical illness, the following actions should be followed in hierarchical order:

- i) For patients with persistent hyperkalemia, defined as [K+] > 5.5 mmol/L at 24 hours after randomization, the treating ICU team can lower the potassium [K+] concentration in the replacement/dialysis solutions, as per ICU-specific protocols.

- ii) For patients with persistent metabolic acidosis, defined as pH <7.25 and BE < -10 at 24 hours after randomization, the treating ICU team can add supplementary bicarbonate (HCO₃) either as a continuous infusion or bicarbonate can be added to the replacement/dialysate solutions, as per ICU-specific protocols.
- iii) For patients who are refractory to the above modifications to the prescribed CRRT or those who have persistent azotemia, defined as [urea] >30 mmol/L at 24 hours after randomization, the treating ICU team can adjust the dose-intensity to the upper limit of dose-intensity within the allocation. For example, in those patients allocated to the low dose-intensity group (target 10 mL/kg/hr), adjust the prescribed dose to 15 mL/kg/hr.

If patients have their CRRT dose-intensity prescription further modified outside their allocated dose-intensity (e.g., a patient allocated to 10-15 mL/kg/hr is increased to >15 mL/kg/hr) for reasons not specified above, this will be considered a protocol deviation. The reason for the dose-intensity modification must be documented and will be classified as: i) inadequate acid-base control; ii) inadequate electrolyte control; iii) inadequate azotemic/metabolic control; and iv) other (describe).

